8.3 Off-Agent Criteria

All participants will be off agent on or before day 364 +/- 7days (52 weeks +/- 1 week) of administration. Participants may stop taking study agent for the following reasons: completed the protocol-prescribed intervention, adverse event or serious adverse event that would compromise the study drug administration or contraindicate the prostate biopsy procedures required in the study, any treatment for prostate cancer between the diagnostic biopsy and end of study biopsy, inadequate agent supply, noncompliance, concomitant medications, or medical contraindication.

8.4 Off-Study Criteria

Participants may go off study for the following reasons: the protocol intervention and any protocol required follow-up period is completed, AE/SAE, lost to follow-up, non-compliance, concomitant medication, medical contraindication, withdrawal of consent, determination of ineligibility, or death. Off study will mean that the investigator will not be able to or does not need to follow the participant to complete any measurements.

8.5 Study Termination

NCI, DCP as the study sponsor has the right to discontinue the study at any time.

9. CORRELATIVE/SPECIAL STUDIES

9.1 Rationale for Methodology Selection

We will perform correlative studies involving the intermediate endpoint biomarkers. As the following will be measured in blood plasma, they will be obtained at baseline and at every 3 months thereafter: Insulin-like growth factor 1 (IGF-1) and IGF binding protein 3 (IGFBP-3) will be measured by immunoassay. PSA will be evaluated in the blood serum.

The following will be measured (using immunohistochemical staining) in benign, normal adjacent to tumor, and tumor tissue obtained from the pre-study and end of study prostate biopsies: PSA, IGF-1, IGFBP-3, apoptosis (CASPASE 3), Ki-67, IGF-1R, and androgen receptor.

9.2 Comparable Methods

We have selected ELISA as a method as it increased sensitivity and quantitation over 2D gels and westerns. **IGF-1.** Assay Summary: IGF-1 in plasma will be measured by a commercially available 96-well plate quantitative sandwich immunoassay from R&D Systems (Minneapolis, MN). The standard curve ranges from 0.188 to 6.0 ng/ml IGF-1. **IGFBP-3.** Assay Summary: IGFBP-3 will be studied in EDTA plasma by a commercially available 96-well plate quantitative sandwich enzyme immunoassay (Quantikine® Human IGFBP-3, R & D Systems, Minneapolis, MN). Findlay et al., (Findlay et al, 2000) recommended precision and accuracy should be in the range of 20-25% for immunoassays and all three assays are well within that range. We have extensive experience with all three assays in human samples.

An important aspect of clinical trials focused on tissue biomarkers is ease and adequacy of tissue acquisition. AS subjects undergo repeat prostate biopsies at intervals of 1-2 years depending on the group and clinical situation. These biopsies are recommended to be 4 quadrant core needle biopsies to a total of 8-12 cores. In an AS population, the majority of the cores will be normal prostate epithelium with scattered amounts of adenocarcinoma and prostatic intraepithelial neoplasia. Therefore, efficiency of use will be paramount. Below are recent technological advances available to UWI consortium studies that improve upon tissue use efficiency (more endpoints assessed with less tissue).

Immunohistochemistry (IHC):

Chromogenic multiplex IHC assay will be used, so the spatial variation of the biomarker expression in the tissue can also be analyzed and compared. Tissue slides will be deparaffinized and stained following standard protocol (Huang, Human Pathology 2013 44(1):29-38). Target markers (PSA, IGF-1, IGFBP-3 apoptosis [CASPASE 3], Ki-67, IGF-1R, and androgen receptor [AR]) will be detected with specific primary antibodies from reputable vendors. The primary antibodies will be paired to perform dual immunostaining to minimize waste of biopsy tissue samples. Standard staining agents will be employed.

Biomarker quantitation:

Vectra™ (Perkin Elmer, Waltham, MA) will be used for quantitation of the biomarkers. This system includes an automated slide scanner and state-of-the-art softwares (Nuance™ and inForm™). Vectra™ is the most advanced instrument for extracting proteomic and morphometric information from tissue microarray or intact tissue sections. Vectra merges automated slide-handling, multispectral imaging technology, and unique pattern-recognition-based image analysis into a powerful system for discovery and clinical studies. This system accurately measures protein or mRNA/DNA targets and morphometric characteristics in distinct tissue regions of interest on whole slides or tissue microarray (TMA). Sections can be labeled with either immunofluorescent (IF) or immunohistochemical (IHC) stains, or in situ hybridization (ISH) or with conventional stains such as H&E and trichrome. With IF or IHC or ISH, single or multiple proteins or mRNA/DNA targets can be measured on a per-tissue, per-cell, and per-cell-compartment (e.g., nuclear, cytoplasmic) basis, even if those signals are spectrally similar, are in the same cell compartment or are obscured by autofluorescence. Vectra™ processes up to 200 slides in a single run or analyze every spot in a TMA.

The process to quantitate target proteins using the Vectra™ is briefly described as follows:

Image acquisition: Briefly, the stained slides will be loaded onto the Vectra slide scanner. A scanning protocol including a spectral library will be created based on the tissue size, areas of interest and staining complexity (single or multiple staining in a single section). 8-bit image cubes will be acquired for analysis. For setting up the spectral library, three control prostate tissue slides with one dye only (DAB dye, Warp red and hematoxylin, respectively) will be prepared and scanned.

Analysis: Each chromogen has its unique spectral characteristics (curve), which is the basis for building the spectral library. First, we will use the Nuance software and image cubes acquired from the control slides to create a spectral library – defining the spectral curve for each chromogen (DAB, Warp red and hematoxylin) used in this experiment. The spectral library will then be used to unmix the signals on the test slides triple-stained with DAB, Warp red and hematoxylin by recognizing their unique spectral curves for quantitation. By such, signal noises and cross talk are eliminated (Figure 1). Then, using the created spectral library and inForm software to do tissue (epithelium vs. stroma, etc.) and cell (nucleus vs. cytoplasm) segmentations (Figure 2). Then the target signals will be quantitated within the selected subcellular compartment(s) of interest. Continuous signal intensity data will be generated.

[figure not shown]

Figure 5. Nuance work area: Left pane shows the spectral library created with pure DAB, pure Warp red and pure hematoxylin slides. Right pane shows an image (top left panel) of prostate adenocarcinoma (PCa) dual immunostained with anti-p27 (brown) and Ki-67 (red) and counter stained with hematoxylin (blue), three unmixing gray images of PCa (DAB, Warp red and hematoxylin, respectively) using the spectral library (3 middle panels) and a composite image (top right panel) of unmixing DAB, Warp red and hematoxylin. Target markers (p27 and Ki-67) are quantitated with unmixing pure signals.

[figure not shown]

Figure 6. Prostate adenocarcinoma tissue. Epithelium (pink) and stroma (green) are segmented. The nuclear (bright green) and cytoplasmic (purple/blue) compartments in the epithelium are also segmented using inFormTM software. Target markers can be quantitated in the segmented subcellular compartments.

10. SPECIMEN MANAGEMENT

10.1 Laboratories

The UWCCC Cancer Pharmacology Laboratory (The CP lab) will be the central repository for research specimens collected by consortium members. The CP lab will prepare kits for distribution to each PO for use in collection of biomarker data. Upon the receipt of blood, urine, and tissue samples, the CP lab will coordinate the distribution of tissue blocks to the study pathologists for evaluation and biomarker analysis. The CP lab will perform all of the plasma biomarker analyses and perform pharmacokinetic analyses on both plasma and urine specimens, as well as the serum Total PSA levels.

The UWCCC Translational Research Initiatives in Pathology (TRIP) lab will serve as the central pathology analytical facility for the prostate tissue samples acquired for this study. The POs will send paraffin-embedded tissue blocks or unstained slides to the CP lab. The CP lab will be responsible for distributing these blocks or slides to the pathology lab. The pathology lab will be responsible for preparing the pathological specimens for analysis.

10.2 Collection and Handling Procedures

At the baseline visit, we will be performing blood and urine pharmacokinetic analyses, plasma biomarker analyses, and total serum PSA and testosterone levels. Pharmacokinetic analyses, plasma biomarker analyses and total serum PSA levels will be done at all subsequent visits. Serum testosterone levels will be done at baseline and Weeks 26 and 52.

To collect the urine specimen: One (1) urine collection cup and four (4) cryovials are required. Collect at least 10 ml of urine. If the participant has difficulty voiding 10 ml of urine, then collect all of the urine the participant can void at one time. You do not need to collect urine from multiple voids to meet the required minimum volume (10ml). Document the date and time of the void, the void volume and the date and time of the previous void.

To process the urine specimen: Aliquot urine into four (4) cryovials. Dispose of any additional urine. Label the tubes with the participant's initials, PID, sample type, time and date of collection.

To store the urine specimen: Freeze the specimens at -70°C . Store the specimens at -70°C until the participant has completed all of the study visits. See section 10.3 for shipping procedures.

To collect the blood specimens: Basic phlebotomy supplies will be in the lab kit provided by the CP lab: green and red top tubes and cryovials as needed. Draw 9mls of blood into each of the green top tubes. Draw 2.5mls of blood into the red top tube(s).

To process the blood specimens: Centrifuge the green top tubes at $\sim 1000\times\text{G}$ for 10-15 minutes. Aliquot the plasma into eight (8) cryovials. Allow the red top tube(s) to clot, then centrifuge at $\sim 1000\times\text{G}$ for 10-15 minutes. If one red top tube is drawn,

aliquot serum equally into two (2) cryovials. If two red top tubes are drawn, aliquot serum equally into four (4) cryovials.

Label cryovials with subject initials, PID, time and date of collection, and sample type (i.e., “baseline” or “Week 13 Visit”, etc.) Freeze at -70° C.

To store the blood specimens: Store the cryovials at -70°C until the participant has completed all of the study visits. See section 10.3 for shipping instructions.

Prostate biopsy specimens:

The POs will request formalin-fixed, paraffin-embedded tissue blocks from the pre-study baseline and end of study prostate biopsies for submission to the 3P Lab. The CLO will review each participant’s pre- and post-intervention pathology report and select the blocks to be submitted for analysis. This will include location matched blocks of entirely benign cores of prostate tissue, location matched blocks with tumor cores and any additional blocks with tumor cores.

Tissue blocks will be returned to the POs pathology department upon request.

If the pathology department holding the biopsy tissue will not release tissue blocks, 10 unstained slides may be substituted. The slides should be cut in 4-5 um-thick sections and picked up on Super Frost Plus or comparably charged slides. These slides should not be pre-melted or baked. If there is insufficient tissue in the block to cut 10 sections, the remaining sections may be cut from another block containing adenocarcinoma (if another block is available from the same biopsy is available).

If the POs pathology department’s policy is not to release blocks immediately after biopsy, the request for blocks may be delayed up to 2 months in order to provide adequate time for pathological processing of the blocks.

Procedure notes and pathology reports: Once the procedure notes and pathology reports are available, blinded copies should be added to the participant’s chart. Additionally, copies should be forwarded to the central lab with the shipment of the participant’s research kit.)

10.3 Shipping instructions

Blood and Urine Specimens

PO’s with a -70° C freezer will batch blood and urine samples and ship all research samples for one participant once that participant has completes the study. If a PO does not have access to a -70°C freezer, they should contact the CLO before enrolling participants so special arrangements can be made for the storage and shipping of research samples.

When a participant completes the study and all blood and urine samples are completely frozen at -70° C, place all of the samples in biohazard bags. Place a layer of dry ice on the bottom of the Styrofoam cooler (included in the lab kit). Place the biohazard bags on top of the ice and cover with enough dry ice to fill the cooler.

Complete the Frozen Sample Shipping Inventory. [contact]) or e-mail ([contact]) a copy of the inventory to the CLO prior to shipping, place a copy on top of the lid of the cooler, and file the original in the participant's study chart. Place the cooler in the cardboard shipping box it arrived in.

Tissue Blocks/Slides (Pre-study/ Baseline and End of Study/Early Termination)

The CLO will send a list of the blocks to be requested to the POs. The PO will request the selected blocks from the pathology department where the biopsy was read. If the pathology department will not release blocks, 10 unstained slides may be substituted (see section 10.2 Collection and Handling Procedures: Prostate biopsy specimens). The PO's will be provided with a Styrofoam shipping container, gel packs and shipping labels and instructions at the time of the request.
For all shipments:

Ship only on a Monday, Tuesday or Wednesday to ensure safe arrival during the week. Do not ship the day before a holiday.

Call [contact]) or E-mail ([contact]) the CP Lab to inform them of the shipment.

Use the express courier service indicated by the shipping label contained in the lab kit. Closely follow all special shipping instructions outlined in the kit instruction packet.

Address to:
CP Lab
University of Wisconsin Hospital and Clinics
[name]
[name]
[name]

10.4 Blood, Urine and Tissue Banking

Biologic specimens collected during the conduct of each clinical trial that are not used during the course of the study will be considered deliverables under the contract and thus the property of the NCI. At study completion, NCI reserves the option to either retain or relinquish ownership of the unused biologic specimens. If NCI retains ownership of specimens, the Contractor shall collect, verify and transfer the requested biologic specimens from the PO to a NCI-specified repository or laboratory at NCI's expense.

11. REPORTING AEs

DEFINITION: An AE is any untoward medical occurrence in a study participant. An AE does not necessarily have a causal relationship with the treatment or study participant. An AE can therefore be any unfavorable and unintended sign (including a clinically significant laboratory finding), symptom, or disease temporally associated with participation in a

study, whether or not related to that participation. This includes all deaths that occur while a participant is on a study.

A list of AEs that have occurred or might occur (Reported Adverse Events and Potential Risks) can be found in Section 6.2, Pharmaceutical Information, as well as the Investigator Brochure or package insert.

11.1 Adverse Events (AEs)

11.1.1 Reportable AEs

All AEs that occur after the informed consent is signed (including those that occur prior to the participant starting study agent) must be recorded on the Adverse Event Tracking Worksheet whether or not related to study agent.

11.1.2 AE Data Elements:

- AE reported date
- AE Verbatim Term
- Common Terminology Criteria for Adverse Events v4.0 (CTCAE) AE term
- Event onset date and event ended date
- Severity grade
- Attribution to study agent (relatedness)
- Whether or not the event was reported as a serious adverse event (SAE)
- Whether or not the subject dropped due to the event
- Action taken with the study agent
- Outcome of the event
- Comments

11.1.3 Severity of AEs

- 11.1.3.1 Identify the adverse event using the NCI Common Terminology Criteria for Adverse Events (CTCAE) version 4.0. The CTCAE provides descriptive terminology and a grading scale for each adverse event listed. A copy of the CTCAE can be found at http://ctep.cancer.gov/protocolDevelopment/electronic_applications/ctc.htm

AEs will be assessed according to the CTCAE grade associated with the AE term. AEs that do not have a corresponding CTCAE term will be assessed according to the general guidelines for grading used in the CTCAE v4.0. as stated below.

CTCAE v4.0 general severity guidelines:

Grade	Severity	Description
1	Mild	Mild; asymptomatic or mild symptoms; clinical or diagnostic observations only; intervention not indicated.
2	Moderate	Moderate; minimal, local or noninvasive intervention indicated; limiting age-appropriate instrumental activities of daily living (ADL)*.
3	Severe	Severe or medically significant but not immediately life-threatening; hospitalization or prolongation of hospitalization indicated; disabling; limiting self-care ADL**.
4	Life-threatening	Life-threatening consequences; urgent intervention indicated.
5	Fatal	Death related to AE.

*Instrumental ADL refers to preparing meals, shopping for groceries or clothes, using the telephone, managing money, etc.

**Self-care ADL refers to bathing, dressing and undressing, feeding self, using the toilet, taking medications, and not bedridden.

11.1.4 Assessment of relationship of AE to treatment

The possibility that the adverse event is related to study agent will be classified as one of the following: not related, unlikely, possible, probable, definite.

11.1.5 Follow-up of AEs

All AEs, including lab abnormalities that in the opinion of the investigator are clinically significant, will be followed according to good medical practices and documented as such.

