7. CLINICAL EVALUATIONS AND PROCEDURES

7.1 Schedule of Events

Evaluation/Procedure	Baseline	Randomization	Week 13 (+/- 1 week) ¹	Week 26 (+/- 1 week) ¹	Week 39 (+/- 1 week) ¹	Week 52 ± 1 Week (or end of study therapy) ¹
Informed consent	x					
Registration	x					
Eligibility Criteria Review	x					
Medical History	x					
Physical Exam	x			x		x
Vital Signs (Temp, BP, Pulse, Respirations) and Weight	x		x	x	x	x
Height	x					
ECOG Performance Status	x					
Assess baseline symptoms	x					
Eligibility/Safety Labs ²	x		x	x	x	x
Total PSA ³	x		x	x	x	x
Randomization		x				
Dispense study medication and diary		x ⁴	x	x	x	
Pill count and drug calendar review			x	x	x	x
Review concomitant medications	x		x	x	x	x
Assess adverse events						x
Prostate Biopsy	x ⁵					x ⁶
The samples listed below will be collected locally, and shipped to UWI for analysis:						
Collect one 3ml red top ⁷	x		x	x	x	x
Collect a second 3ml red top ⁷	x			x		x
Two 10ml green tops ⁷	x		x	x	x	x
Urine collection ⁷	x		x	x	x	x
IHC analysis of normal and abnormal prostate tissue biomarkers (PSA, IGF-1, IGFBP-3, apoptosis [CASPASE 3], Ki-67, IGF-IR, 8OHdG and androgen receptor)	x ⁸					x ⁹

¹The participant must delay his dose of study medication until after blood and urine has been collected, as PK levels need to be assessed approximately 24 hours following the last dose of study medication.

²The following lab tests are to be performed: WBC, Hemoglobin, Platelets, Alkaline Phosphatase, ALT, AST, Total Bilirubin, Serum Creatinine, Sodium, Potassium, Chloride, and Bicarbonate. Eligibility labs must be done \leq 30 days of randomization.

³This total serum PSA will be performed at the PO's clinical lab, and used for clinical purposes.

⁴If the participant is unwilling or unable to return to clinic to pick up study medication, it may be sent overnight by a courier service such as UPS or Fed-Ex.

⁵ The baseline biopsy must have occurred within 13 months prior to the baseline study visit.

⁶The end of study biopsy performed during week 52 ± 1 week or when participant discontinues study therapy. Participant must take study drug the morning of the biopsy after research blood and urine collection but prior to the biopsy.

⁷These blood and urine samples will be used to determine study objectives (PK and biomarker results) as described in §1.2. See §10.2 for collection and processing instructions.

⁸Tissue will be from a biopsy performed within 13 months of study entry

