7.2.7 Baseline Symptoms

Any current/active signs and symptoms experienced by the participant will be documented as Baseline Symptoms. This will include any abnormal laboratory values that are deemed clinically significant. A baseline symptom that increases in grade during the course of the study will be documented as an adverse event. The AE onset date is the date on which the increase in severity occurred.

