7.3 During Study Intervention

7.3.1 At the week 13 and week 39 study visits the following evaluations will be performed: Safety labs and total serum PSA; vital signs and weight; adverse events assessment; review of concomitant medications; compliance assessment; collection of blood and urine for research purposes (plasma and urine pharmacokinetics and serum and plasma biomarkers). The participant will be instructed to delay his dose of study agent on the day of this visit until AFTER blood and urine samples have been collected to allow for a 24-hour post dose pharmacokinetic assessment.

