7.3.1.3 Adverse Event Assessment

The participant will be asked about any symptoms or events he has experienced since initiating study therapy. For each event document a verbatim description of the event, date reported, onset and end dates, CTCAE v4 term and severity grade, the action taken, outcome, whether the event was a Serious Adverse Event or not, whether the participant dropped from the study due to the event and the MD's assessment of attribution of the event to the study agent. Any clinical laboratory results that the M.D. deems clinically significant should be documented as an Adverse Event.

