13.5 Secondary Objectives

For the secondary objectives, we will compare compliance and toxicities for a once daily oral administration over a 12-month period of time between the PFE and placebo groups. We will compare the modulation of the following biomarkers with response to PFE versus placebo: plasma biomarkers, including IGF-1/IGFBP-3 ratio, total serum PSA and normal and abnormal prostate tissue biomarkers, including PSA, IGFBP-3, apoptosis (CASPASE 3), Ki-67, IGF-1R, 8OHdG and androgen receptor. We will also compare PFE constituents/metabolites for evidence of accumulation (trough levels): ellagic acid, dimethyl ellagic acid, dimethyl ellagic acid glucuronide (DMEAG), urolithin A, urolithin A glucuronide, urolithin B and urolithin B glucuronide between the treatment groups. Serum testosterone levels will also be measured.

For secondary objectives, all measurements and changes in measurements of interest will be summarized by treatment arm (and, if applicable, by visit) with appropriate descriptive statistics. Compliance, in terms of the number of pills missed, will be summarized by treatment arm with descriptive statistics, and tested for imbalance using Wilcoxon rank-sum test. Patient toxicity throughout the study will be summarized in several ways; the presence or absence of any toxicities, worst CTCAE grade, and strongest investigator-defined relationship will all be examined and characterized by treatment arm, and analyzed appropriately (Wilcoxon rank-sum for ordinal data, Fisher's exact test for dichotomous data, and log rank test for time to event data). We will examine the differences between the groups for the change from baseline for serum biomarkers, tissue biomarkers, and PFE constituents/metabolites with the appropriate tests; for dichotomous data we will use Fisher's exact test, for ordinal data we will use Wilcoxon rank-sum test, and for continuous data, and a two-sample t-test with normalizing transformation if necessary or Wilcoxon rank-sum test.

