13.9 Interim Analysis

Interim analysis will be performed at a regular schedule to document study progress and to review safety data. This will be performed by an unblinded statistician who is not connected with the day-to-day operation of the study; the regular study staff will not be unblinded. There is no plan for interim analysis for efficacy data. Results of interim analyses of safety data will be reported to the Consortium's data and safety monitoring board for review at approximately six month intervals. They will be in charge of reviewing safety information, including adverse events, serious adverse events, and death data, and making a judgment as to the advisability of continuation. There will be no hard and fast criteria set for the safety analysis.

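### Safety-laboratory changes enter the toxicity comparison only if the site physician calls them clinically significant, and no section specifies a numeric summary of the 12 tests by arm

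*Combined protocol and SAP*

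**What the plan says.** Footnote 2 of the Schedule of Events (7.1) lists the safety tests: "WBC, Hemoglobin, Platelets, Alkaline Phosphatase, ALT, AST, Total Bilirubin, Serum Creatinine, Sodium, Potassium, Chloride, and Bicarbonate". They are done at baseline. For the on-treatment visits, 7.3.1 states: "At the week 13 and week 39 study visits the following evaluations will be performed: Safety labs and total serum PSA". Sections 7.3.2 and 7.4 carry the same tests to weeks 26 and 52.

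Four places govern when a result becomes an adverse event (AE) or a baseline finding:

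- 7.3.1.3, on-study assessment: "Any clinical laboratory results that the M.D. deems clinically significant should be documented as an Adverse Event".
- Section 11, AE definition: an unfavorable sign qualifies, "including a clinically significant laboratory finding".
- 11.1.5, follow-up: "All AEs, including lab abnormalities that in the opinion of the investigator are clinically significant, will be followed according to good medical practices".
- 7.2.7, baseline symptoms: "This will include any abnormal laboratory values that are deemed clinically significant".

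On analysis, 13.5 says that "the presence or absence of any toxicities, worst CTCAE grade, and strongest investigator-defined relationship will all be examined" and compared by arm. Its change-from-baseline tests between arms name serum biomarkers, tissue biomarkers and the PFE constituents and metabolites, but not the safety tests. Section 13.9 puts the board in charge of "reviewing safety information, including adverse events, serious adverse events, and death data".

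**The concern.** Objective 1.2.2 is to assess the toxicity of PFE against placebo over 52 weeks. Section 6.2 notes that the 18-month trial of the same extract had no placebo group, so a placebo-controlled year of blood counts, liver tests, creatinine and electrolytes is worth having. The plan collects these results but leads them into the toxicity comparison through a judgement. Six organizations take part (13.2), and no section says what makes a laboratory value clinically significant.

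The changes most exposed to this filter are low-grade and asymptomatic. A modest shift in one analyte on PFE might be flagged at one site and not at another. The plan does not guarantee any display in which the shift would be visible regardless of flagging.

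**Working it through.** **1. Volume of data.** Tests: 12 (7.1, footnote 2; PSA is listed separately). Post-baseline visits: 4. Men: 30 (13.2).

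- Post-baseline results: 12 x 4 x 30 = 1,440.
- Including baseline: 12 x 5 x 30 = 1,800.

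Both assume full accrual and complete attendance. The documents give no figure of their own for laboratory safety.

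**2. Path of one result.** Take a man whose ALT at entry is above the upper limit of normal but within 1.5 times it, which 4.1.5.2 allows.

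- Baseline: if the value is not deemed clinically significant, 7.2.7 does not make it a baseline symptom.
- On study: the ALT rises and the physician judges the rise not clinically significant. Under 7.3.1.3 and the Section 11 definition no AE is required.
- AE record: the data elements in 11.1.2 (term, grade, attribution) are then not completed for this change.
- Analysis: the change adds nothing to any of the three toxicity summaries in 13.5.

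There is one partial exception. Section 7.2.7 makes a baseline symptom that worsens in grade an AE without repeating the filter. It applies only to abnormalities already judged significant at baseline.

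**3. Filter against grading scale.** The general guidelines in 11.1.3 include in grade 1 asymptomatic findings that are only observed and need no intervention. An isolated laboratory change fits that description, and it is also the kind that a physician may reasonably leave unflagged. The rule for recording can therefore remove values that the scale would grade.

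**4. Texts that could admit the values.**

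| Section | What it offers | What it leaves open |
|---|---|---|
| 13.5, general sentence | Descriptive summaries by arm, and by visit where applicable, for measurements of interest under the secondary objectives | Does not name the safety tests |
| 13.7 | Toxicity evaluation by CTCAE v4.0 for all treated men, with no significance filter | Does not say that unflagged values are graded |
| 12.4 | Committee review of safety data by coded arm, about every 6 months | Does not say that laboratory values are tabulated |

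**5. What 15 men per arm can support.** Section 13.2 needs 14 per group and allows 5% dropout: 14 / 0.95 = 14.7, rounded up to 15, as stated.

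- With no flagged man on placebo, the two-sided Fisher p-value for k flagged on PFE is 2 x C(15,k) / C(30,k).
- k = 4: 2 x 1,365 / 27,405 = 0.100.
- k = 5: 2 x 3,003 / 142,506 = 0.042. So 5 of 15 men must be flagged before p falls below 0.05.
- Testing 12 analytes separately at 0.05, if they were independent, gives a chance of at least one false signal of 1 - 0.95^12 = 0.46.

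These figures argue for a descriptive laboratory table and against formal tests on each analyte.

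**The case against.** Recording only clinically significant laboratory findings as AEs is a defensible convention that limits noise. That stands, and the convention need not change. The follow-up sentence in 11.1.5 is not an analysis rule either; the point rests on 7.3.1.3 read with 13.5.

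The three texts in the table above are real counter-evidence. Toxicity is a secondary objective and the safety tests are its scheduled measurements, so the general sentence in 13.5 can fairly be read to cover them. The list in 13.9 is introduced as non-exhaustive. Sections 12.1 and 12.4 also rely on a Data Management Plan and a Data and Safety Monitoring Plan that are not part of these documents and may specify laboratory listings.

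A reader might infer that laboratory data will play almost no part in the comparison, or that a real drift would be written up as no difference between arms. The documents do not support that, because each of these texts leaves room for the values to be shown.

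A reader might also want to express the gap as lost power, comparing a test on values with a test on flagged men. That is not supportable here. The out-of-range and flagging rates are not in the documents. The 1.10 SD effect in 13.2 is the design effect for IGF-1, not for a laboratory toxicity. The answer also changes greatly between a single visit and the worst of four visits, and 13.5 looks at toxicity throughout the study.

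What remains is that none of the permissive texts names the tests or separates grading from the physician's opinion.

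**Conclusion.** The point holds as a gap in specification. Under the stated recording rule, unflagged low-grade changes in 12 tests at four post-baseline visits do not count in the worst CTCAE grade. Whether the numeric values are compared between arms at all is left to later discretion.

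The extent is the 1,440 planned results, with no stated analysis that is independent of opinion. How many changes would be missed cannot be estimated from the documents. The conclusion assumes that 7.3.1.3 is applied as written and that the two plans not seen here do not already prescribe a laboratory table. It does not depend on any assumed flagging rate. The gap affects objective 1.2.2 only; the IGF-1 analysis and the sample size are untouched.

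**What to change.** Add to 13.5 and 13.7:

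- Each of the 12 scheduled tests is summarized by arm and visit, as value and change from baseline, with a 95% CI for the change.
- Worst post-baseline grade and shift from baseline are tabulated by arm, using the CTCAE v4.0 numeric limits where they exist, regardless of the investigator's opinion.
- The table is descriptive, with no significance tests across the 12 analytes, given 15 men per arm.
- The same table goes to the safety committee by coded arm.

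The AE, SAE and dose-modification rules stay unchanged, and the text should say that the programmed grades serve this table only.

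Before adopting it, confirm that the numeric results are entered in OnCore whether or not they are flagged. Sections 12.1 to 12.3 describe electronic forms and source documents in general terms and do not settle this.

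The cost is a few lines of text, one more table and possibly some data entry; no new blood draws are needed. The downside is small: more low-grade findings will be reported in both arms.
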